## STATISTICAL ANALYSIS PLAN

**Figure 4.1 Cumulative recurrent infection free probability until day 42 from PCR corrected by treatment in Burkina Faso**

**Figure 4.2 Cumulative recurrent infection free probability until day 42 from PCR corrected by treatment in DR Congo**

**Figure 4.3 Cumulative recurrent infection free probability until day 42 from PCR corrected by treatment in Gambia**

**Figure 4.4 Cumulative recurrent infection free probability until day 42 from PCR corrected by treatment in Guinea**

---

**STATISTICAL ANALYSIS PLAN**

---

**Figure 4.5 Cumulative recurrent infection free probability until day 42 from PCR corrected by treatment in Niger**

**Figure 4.6 Cumulative recurrent infection free probability until day 42 from PCR corrected by treatment in Nigeria**

**Figure 4.7 Cumulative recurrent infection free probability until day 42 from PCR corrected by treatment in Tanzania**

**Figure 4.8 Cumulative recurrent infection free probability until day 42 from PCR corrected by treatment in Rwanda**

[figure not shown]
**Figure 4.9 Cumulative recurrent infection free probability until day 42 from PCR corrected by treatment in all sites**

**Table 3a Comparison of Day 63 PCR corrected Efficacy as proportions of Various ACTs with matching TACTs by sites**

Site	PCR corrected ACPR at day 63, n/N, (%)				Risk difference (95% CI, p-value)	
	AL+Placebo (N=XXXX)	AL+AQ (N=XXXX)	ASMQ+Placebo (N=XXXX)	ASMQ + PPQ (N=XXXX)	AL+Placebo vs AL+AQ	ASMQ+Placebo vs ASMQ+PPQ
Burkina Faso	XX/XXX (XX.X)	XX/XXX (XX.X)	XX/XXX (XX.X)	XX/XXX (XX.X)	XX.X (XX.X - XX.X, 0.XXX)	XX.X (XX.X - XX.X, 0.XXX)
DR Congo	XX/XXX (XX.X)	XX/XXX (XX.X)	XX/XXX (XX.X)	XX/XXX (XX.X)	XX.X (XX.X - XX.X, 0.XXX)	XX.X (XX.X - XX.X, 0.XXX)
Gambia	XX/XXX (XX.X)	XX/XXX (XX.X)	XX/XXX (XX.X)	XX/XXX (XX.X)	XX.X (XX.X - XX.X, 0.XXX)	XX.X (XX.X - XX.X, 0.XXX)
Guinea	XX/XXX (XX.X)	XX/XXX (XX.X)	XX/XXX (XX.X)	XX/XXX (XX.X)	XX.X (XX.X - XX.X, 0.XXX)	XX.X (XX.X - XX.X, 0.XXX)
Niger	XX/XXX (XX.X)	XX/XXX (XX.X)	XX/XXX (XX.X)	XX/XXX (XX.X)	XX.X (XX.X - XX.X, 0.XXX)	XX.X (XX.X - XX.X, 0.XXX)
Nigeria	XX/XXX (XX.X)	XX/XXX (XX.X)	XX/XXX (XX.X)	XX/XXX (XX.X)	XX.X (XX.X - XX.X, 0.XXX)	XX.X (XX.X - XX.X, 0.XXX)
Tanzania	XX/XXX (XX.X)	XX/XXX (XX.X)	XX/XXX (XX.X)	XX/XXX (XX.X)	XX.X (XX.X - XX.X, 0.XXX)	XX.X (XX.X - XX.X, 0.XXX)
Rwanda	XX/XXX (XX.X)	XX/XXX (XX.X)	XX/XXX (XX.X)	XX/XXX (XX.X)	XX.X (XX.X - XX.X, 0.XXX)	XX.X (XX.X - XX.X, 0.XXX)

**STATISTICAL ANALYSIS PLAN**

All sites	XX/XXX (XX.X)	XX/XXX (XX.X)	XX/XXX (XX.X)	XX/XXX (XX.X)	XX.X (XX.X - XX.X, 0.XXX)	XX.X (XX.X - XX.X, 0.XXX)
-----------	---------------	---------------	---------------	---------------	---------------------------	---------------------------

[figure not shown]
[figure not shown]

## STATISTICAL ANALYSIS PLAN

**Figure 5 The difference between TACT vs ACT of Day 63 PCR corrected Efficacy as proportions by site****Table 3b Comparison of Day 63 PCR corrected Efficacy using survival methods of Various ACTs with matching TACTs by sites**

Site	PCR corrected ACPR at day 63, Cumulative recurrent infection free percentage (efficacy), % (95% CI)				Hazard ratio (95% CI, p-value)	
	AL+Placebo (N=XXXX)	AL+AQ (N=XXXX)	ASMQ+Placebo (N=XXXX)	ASMQ + PPQ (N=XXXX)	AL+Placebo vs AL+AQ	ASMQ+Placebo vs ASMQ+PPQ
Burkina Faso	XX.X (XX.X - XX.X)	XX.X (XX.X - XX.X)	XX.X (XX.X - XX.X)	XX.X (XX.X - XX.X)	XX.X (XX.X - XX.X, 0.XXX)	XX.X (XX.X - XX.X, 0.XXX)
DR Congo	XX.X (XX.X - XX.X)	XX.X (XX.X - XX.X)	XX.X (XX.X - XX.X)	XX.X (XX.X - XX.X)	XX.X (XX.X - XX.X, 0.XXX)	XX.X (XX.X - XX.X, 0.XXX)
Gambia	XX.X (XX.X - XX.X)	XX.X (XX.X - XX.X)	XX.X (XX.X - XX.X)	XX.X (XX.X - XX.X)	XX.X (XX.X - XX.X, 0.XXX)	XX.X (XX.X - XX.X, 0.XXX)
Guinea	XX.X (XX.X - XX.X)	XX.X (XX.X - XX.X)	XX.X (XX.X - XX.X)	XX.X (XX.X - XX.X)	XX.X (XX.X - XX.X, 0.XXX)	XX.X (XX.X - XX.X, 0.XXX)
Niger	XX.X (XX.X - XX.X)	XX.X (XX.X - XX.X)	XX.X (XX.X - XX.X)	XX.X (XX.X - XX.X)	XX.X (XX.X - XX.X, 0.XXX)	XX.X (XX.X - XX.X, 0.XXX)
Nigeria	XX.X (XX.X - XX.X)	XX.X (XX.X - XX.X)	XX.X (XX.X - XX.X)	XX.X (XX.X - XX.X)	XX.X (XX.X - XX.X, 0.XXX)	XX.X (XX.X - XX.X, 0.XXX)
Tanzania	XX.X (XX.X - XX.X)	XX.X (XX.X - XX.X)	XX.X (XX.X - XX.X)	XX.X (XX.X - XX.X)	XX.X (XX.X - XX.X, 0.XXX)	XX.X (XX.X - XX.X, 0.XXX)
Rwanda	XX.X (XX.X - XX.X)	XX.X (XX.X - XX.X)	XX.X (XX.X - XX.X)	XX.X (XX.X - XX.X)	XX.X (XX.X - XX.X, 0.XXX)	XX.X (XX.X - XX.X, 0.XXX)
All sites	XX.X (XX.X - XX.X)	XX.X (XX.X - XX.X)	XX.X (XX.X - XX.X)	XX.X (XX.X - XX.X)	XX.X (XX.X - XX.X, 0.XXX)	XX.X (XX.X - XX.X, 0.XXX)

## STATISTICAL ANALYSIS PLAN

**Figure 6.1 Cumulative recurrent infection free probability until day 63 from PCR corrected and days by treatment in Burkina Faso**

**Figure 6.2 Cumulative recurrent infection free probability until day 63 from PCR corrected and days by treatment in DR Congo**

**Figure 6.3 Cumulative recurrent infection free probability until day 63 from PCR corrected by treatment in Gambia**

**Figure 6.4 Cumulative recurrent infection free probability until day 63 from PCR corrected by treatment in Guinea**

---

## STATISTICAL ANALYSIS PLAN

---

**Figure 6.5 Cumulative recurrent infection free probability until day 63 from PCR corrected by treatment in Niger**

**Figure 6.6 Cumulative recurrent infection free probability until day 63 from PCR corrected by treatment in Nigeria**

**Figure 6.7 Cumulative recurrent infection free probability until day 63 from PCR corrected by treatment in Tanzania**

**Figure 6.8 Cumulative recurrent infection free probability until day 63 from PCR corrected and days by treatment in Rwanda**

[figure not shown]
**Figure 6.9 Cumulative recurrent infection free probability until day 63 from PCR corrected and days by treatment in all sites**

**Table 4a Comparison of Day 42 PCR uncorrected Efficacy as proportions of Various ACTs with matching TACTs by sites**

Site	PCR uncorrected ACPR at day 42, n/N, (%)				Risk difference (95% CI, p-value)	
	AL+Placebo (N=XXXX)	AL+AQ (N=XXXX)	ASMQ+Placebo (N=XXXX)	ASMQ + PPQ (N=XXXX)	AL+Placebo vs AL+AQ	ASMQ+Placebo vs ASMQ+PPQ
Burkina Faso	XX/XXX (XX.X)	XX/XXX (XX.X)	XX/XXX (XX.X)	XX/XXX (XX.X)	XX.X (XX.X - XX.X, 0.XXX)	XX.X (XX.X - XX.X, 0.XXX)
DR Congo	XX/XXX (XX.X)	XX/XXX (XX.X)	XX/XXX (XX.X)	XX/XXX (XX.X)	XX.X (XX.X - XX.X, 0.XXX)	XX.X (XX.X - XX.X, 0.XXX)
Gambia	XX/XXX (XX.X)	XX/XXX (XX.X)	XX/XXX (XX.X)	XX/XXX (XX.X)	XX.X (XX.X - XX.X, 0.XXX)	XX.X (XX.X - XX.X, 0.XXX)
Guinea	XX/XXX (XX.X)	XX/XXX (XX.X)	XX/XXX (XX.X)	XX/XXX (XX.X)	XX.X (XX.X - XX.X, 0.XXX)	XX.X (XX.X - XX.X, 0.XXX)

### STATISTICAL ANALYSIS PLAN

Niger	XX/XXX (XX.X)	XX/XXX (XX.X)	XX/XXX (XX.X)	XX/XXX (XX.X)	XX.X (XX.X - XX.X, 0.XXX)	XX.X (XX.X - XX.X, 0.XXX)
Nigeria	XX/XXX (XX.X)	XX/XXX (XX.X)	XX/XXX (XX.X)	XX/XXX (XX.X)	XX.X (XX.X - XX.X, 0.XXX)	XX.X (XX.X - XX.X, 0.XXX)
Tanzania	XX/XXX (XX.X)	XX/XXX (XX.X)	XX/XXX (XX.X)	XX/XXX (XX.X)	XX.X (XX.X - XX.X, 0.XXX)	XX.X (XX.X - XX.X, 0.XXX)
Rwanda	XX/XXX (XX.X)	XX/XXX (XX.X)	XX/XXX (XX.X)	XX/XXX (XX.X)	XX.X (XX.X - XX.X, 0.XXX)	XX.X (XX.X - XX.X, 0.XXX)
All sites	XX/XXX (XX.X)	XX/XXX (XX.X)	XX/XXX (XX.X)	XX/XXX (XX.X)	XX.X (XX.X - XX.X, 0.XXX)	XX.X (XX.X - XX.X, 0.XXX)

[figure not shown]

## STATISTICAL ANALYSIS PLAN

[figure not shown]
**Figure 7 The difference between TACT vs ACT of Day 42 PCR uncorrected Efficacy as proportions by site****Table 4b Comparison of Day 42 PCR uncorrected Efficacy using survival methods of Various ACTs with matching TACTs by sites**

Site	PCR uncorrected ACPR at day 42, Cumulative recurrent infection free percentage (efficacy), % (95% CI)				Hazard ratio (95% CI, p-value)	
	AL+Placebo (N=XXXX)	AL+AQ (N=XXXX)	ASMQ+Placebo (N=XXXX)	ASMQ + PPQ (N=XXXX)	AL+Placebo vs AL+AQ	ASMQ+Placebo vs ASMQ+PPQ
Burkina Faso	XX.X (XX.X - XX.X)	XX.X (XX.X - XX.X)	XX.X (XX.X - XX.X)	XX.X (XX.X - XX.X)	XX.X (XX.X - XX.X, 0.XXX)	XX.X (XX.X - XX.X, 0.XXX)
DR Congo	XX.X (XX.X - XX.X)	XX.X (XX.X - XX.X)	XX.X (XX.X - XX.X)	XX.X (XX.X - XX.X)	XX.X (XX.X - XX.X, 0.XXX)	XX.X (XX.X - XX.X, 0.XXX)
Gambia	XX.X (XX.X - XX.X)	XX.X (XX.X - XX.X)	XX.X (XX.X - XX.X)	XX.X (XX.X - XX.X)	XX.X (XX.X - XX.X, 0.XXX)	XX.X (XX.X - XX.X, 0.XXX)
Guinea	XX.X (XX.X - XX.X)	XX.X (XX.X - XX.X)	XX.X (XX.X - XX.X)	XX.X (XX.X - XX.X)	XX.X (XX.X - XX.X, 0.XXX)	XX.X (XX.X - XX.X, 0.XXX)
Niger	XX.X (XX.X - XX.X)	XX.X (XX.X - XX.X)	XX.X (XX.X - XX.X)	XX.X (XX.X - XX.X)	XX.X (XX.X - XX.X, 0.XXX)	XX.X (XX.X - XX.X, 0.XXX)
Nigeria	XX.X (XX.X - XX.X)	XX.X (XX.X - XX.X)	XX.X (XX.X - XX.X)	XX.X (XX.X - XX.X)	XX.X (XX.X - XX.X, 0.XXX)	XX.X (XX.X - XX.X, 0.XXX)
Tanzania	XX.X (XX.X - XX.X)	XX.X (XX.X - XX.X)	XX.X (XX.X - XX.X)	XX.X (XX.X - XX.X)	XX.X (XX.X - XX.X, 0.XXX)	XX.X (XX.X - XX.X, 0.XXX)
Rwanda	XX.X (XX.X - XX.X)	XX.X (XX.X - XX.X)	XX.X (XX.X - XX.X)	XX.X (XX.X - XX.X)	XX.X (XX.X - XX.X, 0.XXX)	XX.X (XX.X - XX.X, 0.XXX)
All sites	XX.X (XX.X - XX.X)	XX.X (XX.X - XX.X)	XX.X (XX.X - XX.X)	XX.X (XX.X - XX.X)	XX.X (XX.X - XX.X, 0.XXX)	XX.X (XX.X - XX.X, 0.XXX)

## STATISTICAL ANALYSIS PLAN

**Figure 8.1** Cumulative recurrent infection free probability until day 42 from PCR uncorrected and days by treatment in Burkina Faso

**Figure 8.2** Cumulative recurrent infection free probability until day 42 from PCR uncorrected and days by treatment in DRC Congo

**Figure 8.3** Cumulative recurrent infection free probability until day 42 from PCR uncorrected by treatment in Gambia

**Figure 8.4** Cumulative recurrent infection free probability until day 42 from PCR uncorrected by treatment in Guinea

**Figure 8.5** Cumulative recurrent infection free probability until day 42 from PCR uncorrected by treatment in Niger

---

## STATISTICAL ANALYSIS PLAN

---

**Figure 8.6 Cumulative recurrent infection free probability until day 42 from PCR uncorrected by treatment in Nigeria**

**Figure 8.7 Cumulative recurrent infection free probability until day 42 from PCR uncorrected by treatment in Tanzania**

**Figure 8.8 Cumulative recurrent infection free probability until day 42 from PCR uncorrected and days by treatment in Rwanda**

[figure not shown]
**Figure 8.9 Cumulative recurrent infection free probability until day 42 from PCR uncorrected and days by treatment in all sites**

**Table 5a Comparison of Day 63 PCR uncorrected Efficacy as proportions of Various ACTs with matching TACTs by sites**

Site	PCR uncorrected ACPR at day 63, n/N, (%)				Risk difference (95% CI, p-value)	
	AL+Placebo (N=XXXX)	AL+AQ (N=XXXX)	ASMQ+Placebo (N=XXXX)	ASMQ + PPQ (N=XXXX)	AL+Placebo vs AL+AQ	ASMQ+Placebo vs ASMQ+PPQ
Burkina Faso	XX/XXX (XX.X)	XX/XXX (XX.X)	XX/XXX (XX.X)	XX/XXX (XX.X)	XX.X (XX.X - XX.X, 0.XXX)	XX.X (XX.X - XX.X, 0.XXX)
DR Congo	XX/XXX (XX.X)	XX/XXX (XX.X)	XX/XXX (XX.X)	XX/XXX (XX.X)	XX.X (XX.X - XX.X, 0.XXX)	XX.X (XX.X - XX.X, 0.XXX)
Gambia	XX/XXX (XX.X)	XX/XXX (XX.X)	XX/XXX (XX.X)	XX/XXX (XX.X)	XX.X (XX.X - XX.X, 0.XXX)	XX.X (XX.X - XX.X, 0.XXX)
Guinea	XX/XXX (XX.X)	XX/XXX (XX.X)	XX/XXX (XX.X)	XX/XXX (XX.X)	XX.X (XX.X - XX.X, 0.XXX)	XX.X (XX.X - XX.X, 0.XXX)
Niger	XX/XXX (XX.X)	XX/XXX (XX.X)	XX/XXX (XX.X)	XX/XXX (XX.X)	XX.X (XX.X - XX.X, 0.XXX)	XX.X (XX.X - XX.X, 0.XXX)

### STATISTICAL ANALYSIS PLAN

Nigeria	XX/XXX (XX.X)	XX/XXX (XX.X)	XX/XXX (XX.X)	XX/XXX (XX.X)	XX.X (XX.X - XX.X, 0.XXX)	XX.X (XX.X - XX.X, 0.XXX)
Tanzania	XX/XXX (XX.X)	XX/XXX (XX.X)	XX/XXX (XX.X)	XX/XXX (XX.X)	XX.X (XX.X - XX.X, 0.XXX)	XX.X (XX.X - XX.X, 0.XXX)
Rwanda	XX/XXX (XX.X)	XX/XXX (XX.X)	XX/XXX (XX.X)	XX/XXX (XX.X)	XX.X (XX.X - XX.X, 0.XXX)	XX.X (XX.X - XX.X, 0.XXX)
All sites	XX/XXX (XX.X)	XX/XXX (XX.X)	XX/XXX (XX.X)	XX/XXX (XX.X)	XX.X (XX.X - XX.X, 0.XXX)	XX.X (XX.X - XX.X, 0.XXX)

[figure not shown]

## STATISTICAL ANALYSIS PLAN

[figure not shown]
**Figure 9 The difference between TACT vs ACT of Day 63 PCR uncorrected Efficacy as proportions by site****Table 5b Comparison of Day 63 PCR uncorrected Efficacy using survival methods of Various ACTs with matching TACTs by sites**

Site	PCR uncorrected ACPR at day 63, Cumulative recurrent infection free percentage (efficacy), % (95% CI)				Hazard ratio (95% CI, p-value)	
	AL+Placebo (N=XXXX)	AL+AQ (N=XXXX)	ASMQ+Placebo (N=XXXX)	ASMQ + PPQ (N=XXXX)	AL+Placebo vs AL+AQ	ASMQ+Placebo vs ASMQ+PPQ
Burkina Faso	XX.X (XX.X - XX.X)	XX.X (XX.X - XX.X)	XX.X (XX.X - XX.X)	XX.X (XX.X - XX.X)	XX.X (XX.X - XX.X, 0.XXX)	XX.X (XX.X - XX.X, 0.XXX)
DR Congo	XX.X (XX.X - XX.X)	XX.X (XX.X - XX.X)	XX.X (XX.X - XX.X)	XX.X (XX.X - XX.X)	XX.X (XX.X - XX.X, 0.XXX)	XX.X (XX.X - XX.X, 0.XXX)
Gambia	XX.X (XX.X - XX.X)	XX.X (XX.X - XX.X)	XX.X (XX.X - XX.X)	XX.X (XX.X - XX.X)	XX.X (XX.X - XX.X, 0.XXX)	XX.X (XX.X - XX.X, 0.XXX)
Guinea	XX.X (XX.X - XX.X)	XX.X (XX.X - XX.X)	XX.X (XX.X - XX.X)	XX.X (XX.X - XX.X)	XX.X (XX.X - XX.X, 0.XXX)	XX.X (XX.X - XX.X, 0.XXX)
Niger	XX.X (XX.X - XX.X)	XX.X (XX.X - XX.X)	XX.X (XX.X - XX.X)	XX.X (XX.X - XX.X)	XX.X (XX.X - XX.X, 0.XXX)	XX.X (XX.X - XX.X, 0.XXX)
Nigeria	XX.X (XX.X - XX.X)	XX.X (XX.X - XX.X)	XX.X (XX.X - XX.X)	XX.X (XX.X - XX.X)	XX.X (XX.X - XX.X, 0.XXX)	XX.X (XX.X - XX.X, 0.XXX)
Tanzania	XX.X (XX.X - XX.X)	XX.X (XX.X - XX.X)	XX.X (XX.X - XX.X)	XX.X (XX.X - XX.X)	XX.X (XX.X - XX.X, 0.XXX)	XX.X (XX.X - XX.X, 0.XXX)
Rwanda	XX.X (XX.X - XX.X)	XX.X (XX.X - XX.X)	XX.X (XX.X - XX.X)	XX.X (XX.X - XX.X)	XX.X (XX.X - XX.X, 0.XXX)	XX.X (XX.X - XX.X, 0.XXX)
All sites	XX.X (XX.X - XX.X)	XX.X (XX.X - XX.X)	XX.X (XX.X - XX.X)	XX.X (XX.X - XX.X)	XX.X (XX.X - XX.X, 0.XXX)	XX.X (XX.X - XX.X, 0.XXX)

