9.4. Randomization and blinding

In Africa, subjects who fulfil all the inclusion criteria and have none of the exclusion criteria will be randomised in an ACT: TACT: TACT: ACT ratio of 1:2:2:1 with the ACT arms consisting out of an ACT and placebo.

The study drug will be provided by the pharmaceutical company in co-blistered or co-packed form in boxes.

The boxes containing artemether-lumefantrine+amodiaquine and artemether-lumefantrine+placebo will be identical, and a combination of both study drugs boxes will be sequentially numbered.

Also, the boxes containing artesunate-mefloquine+piperavaquine and artesunate-mefloquine+placebo will be identical, and a combination of both study drugs boxes will be sequentially numbered.

The absorption of lumefantrine is increased if the artemether-lumefantrine is taken with fat, which increases the efficacy. Therefore artemether-lumefantrine containing arms should be taken with fat.

The absorption of piperavaquine is also increased if it is taken with fat and can hence lead to increased prolongation of the QT/QTc interval. Therefore artesunate-mefloquine containing arms (with PPQ or PBO) should not be taken with fat.

For this reason it is important that the investigator knows whether the allocated treatment should be taken with a fatty snack or drink or not. Therefore the randomization envelope will state that

the allocated treatment potentially contains artemether-lumefantrine or artesunate-mefloquine. However it will not state whether a second partner drug (amodiaquine or piperaquine is included in the treatment). Furthermore the boxes containing either artemether-lumefantrine (+/- amodiaquine) or artesunate-mefloquine (+/- piperaquine) will be clearly distinguishable.

The subjects will be assigned a study arm through a computer-generated randomisation schedule. Individual, sealed and sequentially numbered envelopes will be provided for each trial site with one envelope per patient, indicating whether the treatment for the subject should be taken from the set of artemether-lumefantrine+/-amodiaquine or the artesunate-mefloquine+/-piperaquine containing set. Block randomisation will be used.

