15. STATISTICAL CONSIDERATIONS

15.1. Sample size justification

These studies will have a non-inferiority trial design. Each site will be powered for the efficacy endpoint. For the safety and tolerability endpoint, the sample size will be pooled across the study

sites to achieve the desired power of at least 80% to detect rare events.

For sample size calculations, the following assumptions have been used: The expected efficacy of ACTs (AL, ASMQ) in these countries is expected to be approximately 96%. The matching TACT efficacy is assumed to be at least 90% under the null hypothesis of inferiority based on the WHO 90% efficacy threshold. However preliminary TRACII study data suggest that TACTs potentially may have a better efficacy of 1% to 2% higher in favour of TACT (i.e. a conservative 97%-98% efficacy or higher).

A one-sided alpha of 0.025 has been used in sample size calculations as non-inferiority is in one direction. For the efficacy outcome, a sample size of 60 subjects in the ACT plus placebo arms and 120 subjects in the matching TACT would be needed to achieve approximately 80% power to detect a non-inferiority margin difference between the group efficacy of -6%. With an additional 20% to cover for loss to follow up, we would therefore need 72 subjects in ACT plus placebo group and 144 subjects in the matching TACT in each of the sites. Since there will be 4 arms, it means we will need 432 subjects per site with 144 subjects in the two ACT arms combined and 288 subjects in the two TACT arms combined.

The sample sizes are in the ratio of 1:2 for ACT vs TACT to allow us to collect more safety and tolerability data for TACTs, which could be beneficial to both policy makers as well as future malaria patients [26, 27]. With these numbers of recruited subjects in Africa, we will have a power above 80% to detect an increase of the incidence of adverse events from 1 in 100 to 3 in 100 for subjects treated with ACT as compared to the matching TACT, respectively.

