15.2.1. Proportions

These will be compared using chi squared or Fisher's exact test, as appropriate. Crude proportions will be calculated with the exact 95% confidence intervals (CI), where relevant.

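### SAP 3.3 does not say how the All sites rows of Tables 2a to 5b combine sites; a crude calculation would cost precision and pull hazard ratios towards 1 in the PCR-uncorrected tables if recurrence differs widely between sites

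*SAP*

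**What the plan says.** Protocol 9.4 issues randomisation by site: "Individual, sealed and sequentially numbered envelopes will be provided for each trial site with one envelope per patient". The same section adds that blocks are used. Site is therefore a stratum of the design, although the word is not used.

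The primary objective (Protocol 4.1, SAP 2.1.1) is a comparison within each site, and Protocol 15.1 powers each site separately. SAP Tables 2a to 5b list the eight countries and then add an All sites row. The a-tables give a risk difference and the b-tables a hazard ratio, each with a 95% CI and p-value for both matched pairs. The last of them is titled "Comparison of Day 63 PCR uncorrected Efficacy using survival methods of Various ACTs with matching TACTs by sites".

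The text of SAP 3.3 says that estimates, intervals and p-values will be shown in these tables. It names no method for combining sites: no weights, no site term, no stratified survival model. For proportions, Protocol 15.2.1 says "These will be compared using chi squared or" Fisher's exact test, with no mention of site.

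Rwanda randomises only the AL pair (Protocol 7 and 10.1), so the ASMQ All sites row can hold only seven sites. The SAP table shells nevertheless have ASMQ cells for Rwanda.

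**The concern.** A row with a p-value and no stated method leaves the choice between a crude and a stratified calculation open until the data are seen. The one method that is named for proportions is the crude one.

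The choice matters where risk differs between sites. A crude analysis counts between-site variation as noise, although the design has already removed it from the treatment comparison. It also gives a hazard ratio nearer to 1 than the ratio within each site, because hazard ratios do not collapse over strata with different baseline risk. This is not confounding: allocation within a matched pair is 1:2 at every site.

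The PCR-uncorrected endpoints are where site differences should be largest, because they include reinfection. The protocol expects transmission to differ, since primaquine use depends on whether annual parasite incidence is above or below 50 per 1000. These endpoints define the secondary objective on post-treatment prophylaxis, and the All sites rows are the only pooled estimates of it.

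**Working it through.** **The plan's own figure.** No figure is given for the All sites rows, so the per-site sizes were checked first. Inputs from Protocol 15.1: "The expected efficacy of ACTs (AL, ASMQ) in these countries is expected to be approximately 96"% for ACT; TACT "i.e. a conservative 97%-98% efficacy or higher"; margin 6 points; one-sided 0.025; ratio 1:2. At TACT 98%:

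n(ACT) = (1.960 + 0.842)² × [0.96×0.04 + 0.98×0.02/2] / (0.06 + 0.02)² = 7.85 × 0.0482 / 0.0064 ≈ 59.1, so 60 and 120.

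This reproduces "a sample size of 60 subjects in the ACT plus placebo arms and 120 subjects in the matching TACT", with power 80.6%, at the 98% end of the TACT range. With the stated 20% uplift the numbers are 72 and 144 per site. Totals are 8×72 = 576 and 8×144 = 1152 for the AL pair, and 504 and 1008 for the ASMQ pair (seven sites).

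**Assumptions, not in the documents.** ACT-arm risk by site is evenly spaced over a range, with one common within-site hazard ratio (HR), so that TACT risk = 1 − (1 − ACT risk)^HR.

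**Risk difference.** With K equal sites, and p̄ the mean over sites in each arm:

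- Crude variance = p̄c(1−p̄c)/(K·72) + p̄t(1−p̄t)/(K·144)
- Stratified variance = mean[pc(1−pc)]/(K·72) + mean[pt(1−pt)]/(K·144)

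In each arm the two numerators differ by the between-site variance of p.

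Worked case: 5-50%, HR 0.50, eight sites. Mean risks are 0.275 (ACT) and 0.153 (TACT).

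- Crude: 0.1994/576 + 0.1296/1152 = 0.000459, SE 2.14 points
- Stratified: 0.1777/576 + 0.1220/1152 = 0.000414, SE 2.04 points
- Ratio before rounding: 1.052

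Using 60/120 in place of 72/144 scales both SEs alike and leaves the ratio unchanged.

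**Hazard ratio.** Site hazards are λ = −ln(1 − risk) over follow-up scaled to 1. The large-sample unstratified Cox estimate θ solves Σ [dT − d·YT·θ/(YT·θ + YC)] = 0 over time, with all sites pooled. Here dT and d are TACT and total events, and YT and YC are the numbers at risk. A Cox model stratified by site returns the within-site HR.

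| ACT risk across 8 sites | Within-site HR | CI half-width, crude | CI half-width, stratified | Ratio | Crude HR |
|---|---|---|---|---|---|
| 4% everywhere (PCR-corrected) | 0.75 | 1.88 | 1.88 | 1.000 | 0.750 |
| 1-10% (PCR-corrected) | 0.50 | 2.09 | 2.08 | 1.008 | 0.502 |
| 10-30% | 0.50 | 3.72 | 3.68 | 1.012 | 0.504 |
| 5-50% | 0.50 | 4.20 | 3.99 | 1.052 | 0.516 |
| 5-50% | 1.00 | 4.47 | 4.22 | 1.059 | 1.000 |
| 5-80% | 0.50 | 4.77 | 4.21 | 1.132 | 0.543 |
| 5-80% | 1.00 | 4.94 | 4.29 | 1.152 | 1.000 |

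Half-widths are in percentage points. With seven sites the ratios are almost the same (1.054 at 5-50% and 1.138 at 5-80%, HR 0.50).

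**Simulation.** Eight sites of 72/144, weekly detection, Efron ties, 200 to 300 replicates per run, within-site HR 0.50:

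- 5-80%: crude HR 0.54-0.55 with 84-85% coverage of its 95% CI; stratified HR 0.50 with 92.5-96%.
- 5-50%: crude HR 0.51-0.52, stratified 0.49-0.50; coverage 95-96% for both.

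For the risk difference at 5-70% and HR 0.60 (60/120 per site, 4000 replicates), the crude interval covered 97.5% with eight sites and 96.4% with seven, against 95.4% and 94.7% stratified. The crude risk difference itself showed no bias.

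**The case against.** A reader might infer that the plan ignores site, and that efficacy results throughout Tables 2 to 5 will therefore be distorted. The documents do not support that.

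- **Silence is not a crude analysis.** No sentence says that site is ignored. Protocol 15.2.1 belongs to a section that calls itself a brief overview, concerns proportions only, and is not written for the All sites row. What stands is that the method is unspecified and that the only named tests for proportions are unstratified.
- **Tables 2 and 3 hardly move.** With PCR-corrected failure near 4%, the interval changes by less than 1% and the HR by about 0.002. One qualification: the per-protocol proportions exclude reinfections, so if a TACT prevents reinfection the analysed ratio drifts from 1:2, most at high-transmission sites. Assume no treatment effect on failure, failure 1-10% and ACT reinfection 5-70% rising together across sites, reinfection HR 0.50, and exclusion independent of failure. The crude pooled difference is then off by about 0.5 points (0.2 with failure 2-6%), small against the 6-point margin.
- **No primary result is involved.** The primary comparisons are within site, and no margin or power is attached to an All sites efficacy row. Tables 4 and 5 also show each site.
- **The errors are partly benign.** With 1:2 kept at each site, the crude risk difference is unbiased and its interval is too wide, not too narrow. A null HR stays at 1. The crude HR is also a legitimate marginal quantity; calling it attenuated takes a common within-site HR as the target, which the SAP does not state.
- **The large figures need wide ranges.** The primaquine rule shows that transmission differs, but not that recurrence spans 5-80%. At 5-50% the coverage loss for the HR disappears.

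All of this limits the point. None of it supplies the missing method or gives a reason to prefer the crude one.

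**Conclusion.** The point holds as a minor, free improvement. SAP 3.3 leaves the All sites rows without a method, although randomisation was by site. If they are computed crudely, the loss falls on Tables 4 and 5 and depends on how far recurrence varies between sites: little at 10-30%, modest at 5-50%, and noticeable, including HR coverage of about 85%, only near 5-80%. These sizes rest on assumed, evenly spaced site risks, equal site sizes and one common within-site HR. The PCR-corrected rows are essentially unaffected in the scenarios examined, apart from the small per-protocol drift described above. There is no effect on the within-site primary comparisons.

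**What to change.** In SAP 3.3, state that every All sites row uses:

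- for the a-tables, a site-stratified (Mantel-Haenszel) risk difference with its stratified 95% CI and p-value;
- for the b-tables, a Cox model stratified by site.

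State also that the ASMQ All sites row covers seven sites because Rwanda has no ASMQ arms, and mark the Rwanda ASMQ cells as not applicable.

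The cost is a few lines of SAP wording and one model option. No new data are needed, and no sample size or primary comparison changes. The change should be made before the pooled results are seen.
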